9.1.2 Serious Adverse Events

A *serious AE (SAE)* is any untoward medical occurrence that at any dose:

- results in death
- is life-threatening (defined as an event in which the subject was at risk of death at the time of the event; it does not refer to an event which hypothetically might have caused death if it were more severe)
- requires inpatient hospitalization or causes prolongation of existing hospitalization (see **NOTE** below)
- results in persistent or significant disability/incapacity
- is a congenital anomaly/birth defect
- is an important medical event (defined as a medical event(s) that may not be immediately life-threatening or result in death or hospitalization but, based upon appropriate medical and scientific judgment, may jeopardize the subject or may require intervention [e.g., medical, surgical] to prevent one of the other serious outcomes listed in the definition above.) Examples of such events include, but are not limited to, intensive treatment in an emergency room or at home for allergic bronchospasm; blood dyscrasias or convulsions that do not result in hospitalization.)
- Suspected transmission of an infectious agent (e.g., any organism, virus or infectious particle, pathogenic or non-pathogenic) via the study drug is an SAE.

Although pregnancy, overdose, cancer are not always serious by regulatory definition, these events must be handled as SAEs. (See Section 9.3.6 for reporting pregnancies.)

NOTE: The following hospitalizations are not considered SAEs in BMS clinical studies:

- a visit to the emergency room or other hospital department lasting less than 24 hours that does not result in admission (unless considered an “important medical event” or a life-threatening event)
- elective surgery planned before signing consent
- admissions as per protocol for a planned medical/surgical procedure
- routine health assessment requiring admission for baseline/trending of health status (e.g., routine colonoscopy)
- medical/surgical admission for purpose other than remedying ill health state that was planned before study entry. Appropriate documentation is required in these cases.
- Admission encountered for another life circumstance that carries no bearing on health status and requires no medical/surgical intervention (e.g., lack of housing, economic inadequacy, caregiver respite, family circumstances, administrative).

9.1.3 Nonserious Adverse Events

A *nonserious adverse event* is an AE not classified as serious.

9.2 Assignment of Adverse Event Intensity and Relationship to Investigational Product

The following categories and definitions of causal relationship to investigational product as determined by a physician should be used:

Related: There is a reasonable causal relationship to investigational product administration and the adverse event.

Impact of Daily Prophylaxis Dose Anticoagulation with a Factor Xa Inhibitor (Apixaban) in Patients with Sickle Cell Disease

Not Related: There is not a reasonable causal relationship to investigational product administration and the adverse event.

The expression “reasonable causal relationship” is meant to convey in general that there are facts (e.g., evidence such as de-challenge/re-challenge) or other arguments to suggest a positive causal relationship.

9.3 Collection and Reporting

Adverse events can be spontaneously reported or elicited during open-ended questioning, examination, or evaluation of a subject. (In order to prevent reporting bias, subjects should not be questioned regarding the specific occurrence of one or more AEs.)

If known, the diagnosis of the underlying illness or disorder should be recorded, rather than its individual symptoms. The following information should be captured for all AEs: onset, duration, intensity, seriousness, relationship to investigational product, action taken, and treatment required. If treatment for the AE was administered, it should be recorded in the medical record.

The investigator shall supply the sponsor and Ethics Committee with any additional requested information, notably for reported deaths of subjects.

All AE/SAEs will be reported to the DSMB and BMS. The DSMB will review these data at their regular meeting and notify the Principal Investigator if safety appears to be an issue. After 12 months of this study (or completion of 20 patients, whichever comes first), all of the safety data, including information on any deaths, will be presented to the DSMB in a tabular format. The investigators will also prepare an overall report to accompany the tables. The DSMB will review the report and determine if there is a safety concern. If there are significant adverse events, the DSMB may recommend that the study be terminated. All AE/SAEs will be included in the final study report.

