3.0 Study Design

This is a double blind, parallel group, placebo controlled feasibility study (see figure 1) with an enrollment target of 60 patients (30 per arm). All subjects that meet inclusion criteria as an outpatient, following a 1 month observation, will be randomized to receive an oral prophylactic dose factor Xa inhibitor (Apixaban 2.5mg po bid) or placebo for 6 months. Subjects will return for a 30 day (+/- 5 days) follow-up visit after the End of Treatment (EOT) visit. Initial randomization will occur by computerized randomization technique by the investigational drug services (IDS) at Duke University Medical Center.

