5.2 Data and Statistical Analysis

Sample Size

The same design used in Aim 1 applies to Aim 2. We analyze the change in thrombin generation from enrollment to 2 months following initiation of study drug. We hypothesize that the anticoagulation drug will

Impact of Daily Prophylaxis Dose Anticoagulation with a Factor Xa Inhibitor (Apixaban) in Patients with Sickle Cell Disease

cause a decrease in thrombin generation from baseline to two months. From the literature the standard deviation of the D-dimer measure per patient is 500. With a total of 60 patients randomized equally to each drug sequence, and conservatively assuming no correlation between D-dimer values from baseline to 2 months on the same patient, we achieve a power of 0.863 to detect a mean D-dimer difference in the change from baseline to 2 months between the placebo and the daily prophylactic anticoagulation dose groups of 250 mg/l $\{= [(1000-750) - (1000-1000)] \text{ mg/l}\}$ for a one-sided 0.05 test.

No studies to date have evaluated the influence of anticoagulants on thrombin generation as measured by CAT, therefore sample size and expected differences are calculated based on available studies examining D-dimer.

Statistical Analysis

For our primary outcome, we will compare mean changes in thrombin generation (D-dimer, TAT and phases of CAT) for patients treated with prophylactic dose anticoagulation and placebo. Secondary outcomes will include correlation of hypercoagulable and inflammatory markers to clinical outcomes (such as pain, hospitalization, and number of acute care visits).

In addition, we expect that 50% of the patients to be hospitalized and continue their medication (placebo or drug) as assigned at randomization. For these patients, thrombin generation D-dimer measures will be collected at admission, 3 days and 5 days. Therefore, as a secondary aim, for these hospitalized patients we will analyze the difference between the placebo and drug groups in the change over time in the mean D-dimer values.

Planned Analysis of Primary Endpoint

Following the enrollment of the 60 patients, and completion of the 7 month study period for each patient, all data will be subsequently analysed with the assistance of the Duke Translational Medical Institute. [name] is our lead statistician who will continue to provide statistical support and analysis through this study.

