7.0 Study Duration

Enrollment for this study will be completed within the first 12 months (average 5 patients per month), followed by 8 months to allow completion of study by all patients.

8.0 Data and Safety Monitoring Board.

The Duke University Data and Safety Monitoring Board (DSMB) is a Committee that has been established for the purpose of monitoring clinical studies. The DSMB has multiple responsibilities including:

- Assessing risk and complexity of those clinical trials that have been submitted for review
- Determining the appropriate level of data and safety monitoring
- Reviewing the reports of all serious adverse events (SAEs) that have been experienced by participants in those active clinical trials that are being monitored by the DSMB
- Reviewing the regularly submitted (usually at least yearly) data and safety monitoring reports that are required of all active clinical trials.
- Recommending appropriate actions (closure, increased monitoring, etc.) to the Principal Investigator.

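### At planned accrual, the one tabulated DSMB safety review with a set trigger falls at month 11 to 12, with 55 to 60 of 60 patients enrolled, so it can barely affect enrolment

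*Combined protocol and SAP*

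**What the plan says.** Section 9.3 of the combined protocol and SAP fixes one tabulated review: "After 12 months of this study (or completion of 20 patients, whichever comes first), all of the safety data" go to the DSMB in tables with a report from the investigators, and the board may then recommend termination.

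Section 7.0 sets the calendar: "Enrollment for this study will be completed within the first 12 months (average 5 patients per month), followed by 8 months" for the last patients to finish. Section 3.0 gives the size, "enrollment target of 60 patients (30 per arm", and the treatment length, "or placebo for 6 months", after one month of observation. It also says: "Subjects will return for a 30 day (+/- 5 days) follow-up visit after the End of Treatment (EOT) visit".

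Other oversight is described. Section 9.3 sends all AEs and SAEs to the DSMB, which looks at them when it regularly meets and alerts the investigator to any safety problem. Section 8.0 has the board review SAE reports and periodic monitoring reports, the latter "usually at least yearly", and lets it recommend closure or closer monitoring. None of these has a stated date or patient count, and enrolment is not tied to any of them.

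**The concern.** A trigger worded as the earlier of a date and a number of completers suggests that the board will see aggregate safety data while the trial is still recruiting. Here each patient takes 7 to 8 months to complete and enrolment lasts 12 months. The 20th completion and the end of enrolment therefore nearly coincide.

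Aggregation matters in this population. Section 9.1.2 counts inpatient hospitalisation as an SAE and states no exemption for pain crises, and Section 5.2 expects half the patients to be hospitalised. Against that background, an excess of events is hard to see from individual reports. If the tables arrive when recruitment is nearly over, they can do little to limit the number of patients enrolled.

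**Working it through.** **Inputs**
- Target 60 patients (Section 3.0). Accrual 5 per month for 12 months, then 8 months to finish (Section 7.0).
- One month of observation, 6 months on drug or placebo, about one month of follow-up (Section 3.0).
- Time from enrolment to completion, L. The plan does not define completion. L = 7 months if it means end of treatment (Section 5.2: "completion of the 7 month study period for each patient"), or 8 months if it means the follow-up visit.
- Loss, d: 0 or 20%. Section 4.2 allows 20% for incomplete data, loss to follow-up and dropout together. Treating all of it as non-completion is an assumption.
- The 12 months are assumed to run from first enrolment. Accrual is taken as linear.

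**The plan's own figures.** 5 × 12 = 60 patients, and 1 + 6 + 1 = 8 months per patient. Both agree with Section 7.0.

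**Timing of the review.** Review month = min(12, 20 / [5(1 − d)] + L). Enrolled = min(60, 5 × month). Started drug or placebo = 5 × (month − 1).

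| L | d | 20th completer | Review | Enrolled | Started |
|---|---|---|---|---|---|
| 7 | 0 | 4 + 7 = month 11 | month 11 | 55 | 50 |
| 7 | 20% | 5 + 7 = month 12 | month 12 | 60 | 55 |
| 8 | 0 | 4 + 8 = month 12 | month 12 | 60 | 55 |
| 8 | 20% | 5 + 8 = month 13 | month 12 | 60 | 55 |

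The number randomised depends on a conflict in the plan. Sections 5.1 and 6.1 place randomisation before the observation month, which gives 55 to 60. Section 3.0 places it after, which gives 50 to 55.

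With random (Poisson) accrual averaging 5 per month, 20,000 simulated trials over the same four cases gave a median of 54 to 59 enrolled at the review, with 5th percentiles of 45 to 47.

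**Who could still benefit.** With no dropout:
- Month 11: 20 patients past treatment, 30 on treatment, 5 in observation, 5 not enrolled.
- Month 12: 25 past treatment, 30 on treatment, 5 in observation.

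Planned exposure is 60 × 6 = 360 patient-months over both arms. At month 11 it is 20 × 6 + 30 × 3 = 210 (58%). At month 12 it is 25 × 6 + 30 × 3 = 240 (67%).

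**Other accrual rates (r per month; assumptions, no dropout).** With L = 7, completers come before month 12 only if 20/r + 7 < 12, that is r > 4. By then more than 20 + 7 × 4 = 48 are enrolled. With L = 8 the condition is r > 5, by which time all 60 are enrolled. At slower rates the 12-month date governs: 4 × 12 = 48 enrolled at 4 per month, and 3 × 12 = 36 at 3 per month.

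**Trigger at 20 patients with one month on study drug.** Month = 20/r + 1 + 1. Enrolled = 20 + 2r.
- 5 per month: month 6, 30 enrolled.
- 4 per month: month 7, 28 enrolled.
- 3 per month: month 8.7, 26 enrolled.

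At month 6, 25 patients have started. Exposure is 5 × 5² / 2 = 62.5 patient-months, or 17% of 360.

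**The case against.** The strongest reply is that the board does not depend on this table. It receives every AE and SAE, considers them at its regular meetings, and can recommend closure without waiting for the tabulated review. Section 8.0 also leaves the level of monitoring to the board, so it could ask for an earlier table without a protocol change. This stands. A reader might infer that there is no DSMB oversight during enrolment, and the documents contradict that. What remains is that no meeting date or patient count is given, and that yearly reporting guarantees nothing before month 12.

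A reader might also infer that essentially all patients will have been exposed by the time of the review. That does not follow either: 50 to 55 have started, about 30 of them are mid-treatment, and 33% to 42% of planned exposure is still to come. Nor is the completer trigger wholly redundant, since on the end-of-treatment reading it brings the review forward by a month.

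Two further limits are fair. Section 9.3 does not say that the tables are split by arm, so it cannot be assumed that the review is comparative. An earlier table would also be thinner, and nothing in the documents requires a tabulated look at mid-enrolment.

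**Conclusion.** The point holds as one about the timing of the only tabulated review with a stated trigger. At planned accrual that review comes at month 11 to 12, with 0 to 5 of 60 patients left to enrol, so it can barely affect enrolment. It can still protect about 30 patients on treatment and 5 to 10 not yet started.

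The result rests on 5 patients per month, on the 12 months running from first enrolment, and on completion meaning 7 or 8 months. At an assumed 3 to 4 per month, the 12-month date would fall with 36 to 48 enrolled, and the review would then have some influence on recruitment. This is a worthwhile improvement to the plan and not a failure of safety oversight.

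**What to change.** In Section 9.3, trigger the first tabulated review when 20 patients have completed one month on study drug, and keep the 12-month review as the second. At planned accrual this puts an aggregate table before the board at about month 6, with about 30 of 60 enrolled. In the same edit, state when the 12 months start, and reconcile Section 3.0 with Sections 5.1 and 6.1 on when patients are randomised.

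The cost is one more safety table for an existing board. Its limitation is exposure: about 62 of 360 planned patient-months, against 210 to 240 at month 11 to 12. That is why the later review should stay.

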9.3.1 Serious Adverse Events

Following the subject’s written consent to participate in the study, all SAEs must be collected, including those thought to be associated with protocol-specified procedures. All SAEs must be collected that occur within 70 days of discontinuation of dosing of the investigational product. If applicable, SAEs must be collected that relate to any later protocol-specified procedure (e.g., a follow-up skin biopsy). The investigator should notify BMS of any SAE occurring after this time period that is believed to be related to the investigational product or protocol-specified procedure.

All SAEs whether related or unrelated to the study drug, apixaban, must be immediately reported to BMS (by the investigator or designee) within 24 hours of becoming aware of the event. If only limited information is initially available, follow-up reports are required. The original SAE form must be kept on file at the study site.

All SAEs should be faxed or emailed to BMS at:

Global Pharmacovigilance & Epidemiology
Bristol-Myers Squibb Company
[contact]
Email: [contact]

Impact of Daily Prophylaxis Dose Anticoagulation with a Factor Xa Inhibitor (Apixaban) in Patients with Sickle Cell Disease

Serious adverse events, whether related or unrelated to investigational product, must be recorded on the SAE page and reported expeditiously to BMS (or designee) to comply with regulatory requirements. An SAE report should be completed for any event where doubt exists regarding its status of seriousness.

All SAEs must be immediately reported by confirmed facsimile transmission (fax) and mailing of the completed SAE page. In some instances where a facsimile machine is not available, overnight express mail may be used. If only limited information is initially available, follow-up reports are required. (Note: Follow-up SAE reports should include the same investigator term(s) initially reported.) In selected circumstances, the protocol may specify conditions that require additional telephone reporting.

If the investigator believes that an SAE is not related to the investigational product, but is potentially related to the conditions of the study (such as withdrawal of previous therapy, or a complication of a study procedure), the relationship should be specified in the narrative section of the SAE page.

If an ongoing SAE changes in its intensity or relationship to the investigational product, a follow-up SAE report should be sent immediately to the sponsor. As follow-up information becomes available it should be sent immediately using the same procedure used for transmitting the initial SAE report. All SAEs should be followed to resolution or stabilization.

9.3.2 Handling of Expedited Safety Reports

In accordance with local regulations, BMS will notify investigators of all SAEs that are suspected (related to the investigational product) and unexpected (i.e., not previously described in the Investigator Brochure). In the European Union (EU), an event meeting these criteria is termed a Suspected, Unexpected Serious Adverse Reaction (SUSAR). investigator notification of these events will be in the form of an expedited safety report (ESR).

Other important findings which may be reported by the sponsor as an ESR include: increased frequency of a clinically significant expected SAE, an SAE considered associated with study procedures that could modify the conduct of the study, lack of efficacy that poses significant hazard to study subjects, clinically significant safety finding from a nonclinical (e.g., animal) study, important safety recommendations from a study data monitoring committee, or sponsor decision to end or temporarily halt a clinical study for safety reasons.

Upon receiving an ESR from BMS, the investigator must review and retain the ESR with the Investigator Brochure. Where required by local regulations or when there is a central IRB/IEC for the study, the sponsor will submit the ESR to the appropriate IRB/IEC. The investigator and IRB/IEC will determine if the informed consent requires revision. The investigator should also comply with the IRB/IEC procedures for reporting any other safety information.

In addition, suspected serious adverse reactions (whether expected or unexpected) shall be reported by BMS to the relevant competent health authorities in all concerned countries according to local regulations (either as expedited and/or in aggregate reports).

Impact of Daily Prophylaxis Dose Anticoagulation with a Factor Xa Inhibitor (Apixaban) in Patients with Sickle Cell Disease

9.3.3 Nonserious Adverse Events

The collection of nonserious AE information should begin at initiation of investigational product. Nonserious AE information should also be collected from the start of a placebo lead-in period or other observational period intended to establish a baseline status for the subjects.

If an ongoing nonserious AE worsens in its intensity, or if its relationship to the investigational product changes, a new nonserious AE entry for the event should be completed. Nonserious AEs should be followed to resolution or stabilization, or reported as SAEs if they become serious. Follow-up is also required for nonserious AEs that cause interruption or discontinuation of investigational product, or those that are present at the end of study participation. Subjects with nonserious AEs at study completion should receive post-treatment follow-up as appropriate.

All identified nonserious AEs must be recorded and described in the medical record.

9.3.4 Laboratory Test Abnormalities

All laboratory test results captured as part of the study should be recorded following institutional procedures. Test results that constitute SAEs should be documented and reported as such.

The following laboratory abnormalities should be documented and reported appropriately:

- any laboratory test result that is clinically significant or meets the definition of an SAE
- any laboratory abnormality that required the subject to have study drug discontinued or interrupted
- any laboratory abnormality that required the subject to receive specific corrective therapy.

9.3.5 Overdose

An overdose is defined as the accidental or intentional administration of any dose of a product that is considered both excessive and medically important. All occurrences of overdose must be reported as an SAE.

9.3.6 Pregnancy

Sexually active WOCBP must use an effective method of birth control during the course of the study, in a manner such that risk of failure is minimized. Before enrolling WOCBP in this clinical study, the investigator must review the guideline about study participation for WOCBP which can be found in the GCP Manual for Investigators. The topics include the following:

- General Information
- Informed Consent Form
- Pregnancy Prevention Information Sheet

- Drug Interactions with Hormonal Contraceptives
- Contraceptives in Current Use
- Guidelines for the Follow-up of a Reported Pregnancy.

Before study enrollment, WOCBP must be advised of the importance of avoiding pregnancy during study participation and the potential risk factors for an unintentional pregnancy. The subject must sign an informed consent form documenting this discussion.

Impact of Daily Prophylaxis Dose Anticoagulation with a Factor Xa Inhibitor (Apixaban) in Patients with Sickle Cell Disease

All WOCBP MUST have a negative pregnancy test within 72 hours before receiving apixaban. The minimum sensitivity of the pregnancy test must be 25 IU/L or equivalent units of HCG. If the pregnancy test is positive, the subject must not receive apixaban and must not be enrolled in the study.

In addition, all WOCBP should be instructed to contact the investigator immediately if they suspect they might be pregnant (e.g., missed or late menstrual period) at any time during study participation.

If, following initiation of the investigational product, it is subsequently discovered that a study subject is pregnant or may have been pregnant at the time of investigational product exposure, including during at least 6 half-lives after product administration, the investigational product will be permanently discontinued in an appropriate manner (e.g., dose tapering if necessary for subject safety). The investigator must immediately notify BMS of this event and record the pregnancy on the Pregnancy Surveillance Form (not an SAE form). Initial information on a pregnancy must be reported immediately to BMS, and the outcome information provided once the outcome is known. Completed Pregnancy Surveillance Forms must be forwarded to BMS according to SAE reporting procedures.

Any pregnancy that occurs in a female study participant or a female partner of a male study participant should be reported to the sponsor. Information on this pregnancy will be collected on the Pregnancy Surveillance Form. Protocol-required procedures for study discontinuation and follow-up must be performed on the subject unless contraindicated by pregnancy (e.g., x-ray studies). Other appropriate pregnancy follow-up procedures should be considered if indicated. The study staff will continue to follow the pregnant female throughout the course of the pregnancy until an outcome is known. In addition, the investigator must report to BMS and follow-up on information regarding the course of the pregnancy, including perinatal and neonatal outcome. Infants should be followed for a minimum of 8 weeks.

The study staff will continue to follow you throughout the course of the pregnancy, including perinatal and neonatal until an outcome is known. The study staff will collect information for your infant(s) from the medical chart and through phone contact with the parent/parents. The information will include any complications or abnormalities at birth. The study staff will also document the following information: date of birth, sex, birth weight, head circumference and Apgar score (**A**ppearance, **P**ulse, **G**rimace, **A**ctivity, **R**espiration). The study staff will continue to collect information about your infant for a minimum of 8 weeks after birth.

